## 7.9.3 Smoking Pack-Years

Cigarette smoking pack-years are calculated by multiplying the number of packs of 20 cigarettes smoked per day by the number of years the person has smoked. For example, one pack year is equal to smoking one pack per day for 1 year, or two packs per day for half a year, and so on.

Table 4: Estimation of Smoking Pack-Years of Non-tobacco Products

CONFIDENTIAL Page 46 of 68

#### 8. TRIAL ASSESSMENTS

## 8.1 Assessment of Efficacy

## 8.1.1 Key Secondary Efficacy Assessment

Objective cough counts measured as 24-hour sound recordings using a custom-built digital recording device. The key secondary efficacy endpoint is the change from baseline in awake cough frequency, calculated as the (total cough count while awake)/(duration awake) and expressed in hours. For each treatment period, baseline is the cough frequency during the recorder assessment just prior to initiation of investigational product.

## 8.1.2 Secondary Efficacy Assessments

Secondary efficacy assessments are:

- The change from baseline in 24-hour cough frequency will be assessed from the same 24-hour cough monitoring used to measure awake cough frequency.
- Cough severity measured using a 100 mm VAS. Subjects will be asked to rate their cough severity over the previous 2 weeks at screening, and over the previous 24 hours at other timepoints.
- Global rating of change scores for cough frequency and severity.
- Patient Global Impression of Change: A rating scale completed by subjects to assess change in cough frequency since commencing trial medication. It consists of a 7-point scale ranging from "very much improved" to "very much worse."
- Clinician Global Impression of Change: A rating scale completed by Investigators to assess the subject's response to the trial treatment. It consists of a 7-point scale ranging from 'very much improved' to "very much worse."
- Quality of life will be assessed using the LCQ, which is a cough-specific assessment (Birring et al., 2003b). The LCQ comprises three, 7-point domain scores: physical, psychological, and social. A higher score indicates a better quality of life.
- Quality of life will be further be assessed using the CQLQ.

#### 8.2 Pharmacokinetic, Pharmacodynamic, and Other Measurements

There are no PK, pharmacodynamics, or other assessments in this trial.

## 8.3 Assessment of Safety

Safety will be assessed by physical examination and monitoring of AEs, laboratory safety parameters, vital signs, and standard 12-lead ECGs. Unscheduled assessments will be performed if clinically warranted by the Investigator or designee.

CONFIDENTIAL Page 47 of 68

#### 8.3.1 Adverse Events

All AEs occurring during the trial, from the time the subject signs informed consent until the subject completes the trial, will be reported. Any SAEs that occur within 30 days of the end of treatment will also be reported. SAEs will be reported to the regulatory authorities and Institutional Review Boards (IRBs)/Research Ethics Boards (REBs) according to local regulations and will be followed up until the event is resolved or stabilized.

#### 8.3.1.1 Definitions

An AE is defined as any untoward medical occurrence in a clinical investigation subject administered a pharmaceutical product and which does not necessarily have a causal relationship to this treatment. An AE can therefore be any unfavorable and unintended sign (including an abnormal laboratory finding), symptom or disease temporally associated with the use of a medicinal (investigational) product, whether or not related to the treatment administered.

An SAE is defined as any untoward medical occurrence that at any dose:

- Results in death, or
- Is life-threatening, i.e., the subject was at immediate risk of death at the time of the event, or
- Requires in-patient hospitalization or prolongation of existing hospitalization, or
- Results in persistent or significant disability or incapacity, or
- Is a congenital anomaly/birth defect; or
- Is an important medical event, i.e., may not be immediately life-threatening or result in death or hospitalization but may jeopardize the subject or may require intervention to prevent one of the other outcomes listed above. Examples of such events are: bronchospasms requiring intensive treatment in an emergency room or at home, blood dyscrasias, or convulsions that do not result in hospitalization. Development of cancer, drug dependency, or drug abuse are most often considered as SAEs.

The following are not considered to be SAEs:

- Any elective procedures that require admission to hospital as well as any planned elective procedures (e.g., angioplasty) planned prior to signing the inform consent form, unless the underlying condition has worsened or the procedure results in a worsening of the subject's condition. Such conditions should be recorded in the subject's medical history.
- A visit to an emergency room or other hospital department for <24 hours that does not result in admission to hospital unless the reason is considered to be an important medical event or a life-threatening event. These should be recorded as AEs.

CONFIDENTIAL Page 48 of 68

## 8.3.1.2 Adverse Event Reporting

[figure not shown]
Adverse events will be collected with a non-leading question at each visit: "Have you experienced any change in your health or in your general condition since your last visit?" as well as by reporting those events directly observed and spontaneously reported by the subject. Clearly related signs, symptoms, and abnormal diagnostic procedures should preferably be grouped together and recorded as a single diagnosis or syndrome whenever possible. Intensity (mild, moderate, or severe) and relationship to trial treatment (related or unrelated) as well as action taken, seriousness and outcome should be recorded in the AE page of eCRF. Start and end date and time of the event will also be recorded as precisely as possible.

Abnormal laboratory values or vital signs abnormalities are to be recorded as AEs only if they are medically relevant, i.e., symptomatic, requiring corrective treatment, leading to discontinuation or fulfill a criterion for an SAE.

In the case of chronic disease, if the disease is known and documented when the subject enters the trial, only worsening (increased frequency or intensity of the episodes) will be documented as an AE.

## Severity

Severity of an AE is defined as a qualitative assessment of the degree of intensity of an AE as determined by the Investigator or reported by the subject. The assessment of severity is made irrespective of relationship to trial procedures or seriousness of the event and should be evaluated according to the following scale:

## Relationship to Trial Treatment

Assessment of causality is based on the following considerations: associative connections (time or place), pharmacological explanations, previous knowledge of the drug, presence of characteristic clinical or pathological phenomena, exclusion of other causes, or absence of alternative explanations.

The Investigator will assess the causal relationship to the trial treatment according to the following classifications:

• Definite: A clinical event, including laboratory test abnormality, occurring in a plausible time relationship to drug administration and which cannot be explained by concurrent disease or other

CONFIDENTIAL Page 49 of 68

drugs or chemicals. The response to withdrawal of the drug (de-challenge) should be clinically plausible. The event must be definitive pharmacologically or phenomenologically using a satisfactory re-challenge (the drug is readministered to determine if the same reaction occurs) procedure if necessary.

- Probable: A clinical event, including laboratory test abnormality, occurring in a plausible time relationship to drug administration and which cannot be explained by concurrent disease or other drugs or chemicals. The response to withdrawal of the drug (de-challenge) should be clinically plausible.
- Possible: A clinical event, including laboratory test abnormality, with a reasonable time sequence to the drug administration, but which could also be explained by concurrent disease or other drugs or chemicals. Information on drug withdrawal may be lacking or unclear.
- Unlikely ("Not related"): A clinical event, including laboratory test abnormality, with a temporal relationship to drug administration which makes a causal relationship improbable and in which other drugs, chemicals or underlying disease provide plausible explanations.
- Not related: Any event that does not meet the above criteria; there is sufficient information that etiology of the event is in no relation to the trial treatment.

## **Action Taken with Investigational Product**

The Investigator will be asked to record action taken in relation to the trial or trial treatment and to other treatments. The categories in relation to the trial or trial treatment are:

- No action taken
- Investigational product dose reduced
- Investigational product discontinued temporarily
- Investigational product discontinued permanently
- Not applicable

#### Outcome

The Investigator will be asked to record the outcome by choosing one of the following alternatives:

- Recovered
- Recovering
- Not recovered
- Recovered with sequelae
- Unknown

## 8.3.1.3 Reporting of Serious and Significant Adverse Events

Any new and unexpected AEs must be reported to the IRB/REB as required by local regulations.

CONFIDENTIAL Page 50 of 68

Suspected unexpected serious adverse reactions (SUSARs) are AEs that are considered by the Investigator and Sponsor to be related to trial treatment and are both unexpected (i.e., the nature or severity is not expected from the information provided in the Investigator Brochure) and serious. ADX-629 is at an early stage of development, therefore, any SAE deemed related to the trial treatment will be considered unexpected and will be reported as a SUSAR.

The Investigator must complete and submit an SAE report for all SAEs, regardless of the causal relationship to trial treatment as soon as possible, in any case within 24 hours of having received information on the event. The initial report can be followed by a follow-up report as soon as the Investigator obtains more specific information on the event. Every effort should be made to document further any SAE that is fatal or life-threatening within 1 week (7 days) after the initial notification.

The Investigator must also send (preferably by email or fax) copies of all examinations carried out and the dates on which these examinations were performed, to \_\_\_\_\_\_\_, the Sponsor's representative:

Laboratory reference ranges should be included for all laboratory results.

Care should be taken to ensure that the subject's identity is protected and the subject's identifiers in the clinical trial are not included on any copy of source documents provided to the Sponsor.

Suspected unexpected serious adverse reactions are subject to expedited reporting to the Regulatory Authorities and IRB/REB as appropriate. Investigators will be notified by the Safety Management of all SAEs that require prompt submission to their IRB/REB. Investigators should provide written documentation of IRB/REB notification for each report to the Sponsor or will ensure that the appropriate regulatory authorities are notified of all reportable SAEs.

The Sponsor or Sponsor's representative may make expedited reports of all SAEs that are expected and causally related to the IP to the Competent Authorities, according to local regulations.

#### 8.3.1.4 Discontinuation Due to Adverse Events

The onset of an AE is not necessarily a reason for premature withdrawal from the trial or for temporary or permanent discontinuation of trial treatment. If the Investigator decides to discontinue trial treatment permanently because of an AE, this must be documented in the eCRF.

CONFIDENTIAL Page 51 of 68

## 8.3.1.5 Follow-up of Adverse Events

The Investigator must ensure that follow-up of the subject is appropriate to the nature of the event, and that it continues until resolution or until agreed with the Sponsor.

The Investigator should take all appropriate measures to ensure the safety of the subjects. In particular, he or she should follow-up the outcome of any AEs until they return to normal, or the subject's condition stabilizes.

If the Investigator learns of an SAE during the 30 days after the subject's final trial visit and if the Investigator considers the SAE to be causally related to the IP, this should be reported to the Sponsor within 1 day.

## 8.3.2 Pregnancy

In the event of pregnancy, the IP must be discontinued, and the Sponsor informed immediately (i.e., within 1 working day).

Pregnancy in a female trial subject, or in a female partner of a male trial subject, during the trial period or within 4 weeks after the last dose of IP, must be reported to the Sponsor on the pregnancy reporting form within 24 hours of knowledge of its occurrence by the investigative site staff. The pregnancy will be followed up until the outcome has been determined. Any SAE experienced during pregnancy, or if the outcome of the pregnancy is a congenital anomaly or birth defect, the procedure for reporting SAEs (Section 8.3.1.3) will be followed.

#### 8.3.3 Clinical Laboratory Analysis

The following clinical laboratory safety assessments will be performed at the times indicated in the schedule of assessments (Table 1).

Safety Laboratory Tests:

- Hematology: hemoglobin, hematocrit, mean corpuscular volume (MCV), mean corpuscular hemoglobin (MCH), mean corpuscular hemoglobin concentration (MCHC), red blood cell (RBC) count, white blood cell count with differential (neutrophils, lymphocytes, monocytes, eosinophils, and basophils), and platelet count.
- Serum biochemistry: ALT, AST, alkaline phosphatase, gamma-glutamyl transferase, bilirubin (total, direct, and indirect), sodium, potassium, chloride, glucose, blood urea nitrogen, creatinine, albumin, amylase, uric acid, creatine kinase, calcium, magnesium, bicarbonate, lactate dehydrogenase, triglycerides, HDL cholesterol, and low-density lipoprotein cholesterol, and eGFR/1.73 m^2 CKD-EPI.

CONFIDENTIAL Page 52 of 68

• Urinalysis: Albumin, creatinine, bilirubin, glucose, ketones, blood, nitrite, pH, protein, specific gravity, and microscopy (if indicated by macroscopic findings). Spot urine protein to creatinine ratio (sUPCR) will also be performed.

*Pregnancy Tests*: Women of childbearing potential will have a serum pregnancy test at screening, and urine pregnancy tests before the first dose at the start of each treatment period (Visit 3 and Visit 7). FSH will be measured at screening only in females thought to be menopausal if pregnancy status is unknown.

Serologies for HIV, Hepatitis B, and Hepatitis C: HIV Ab, HbsAg, HbsAb, and HCV Ab (screening only).

*SARS-CoV-2*: Specimens for SARS-CoV-2 testing will be analyzed centrally.

*Urine Drug Screen*: Tests for amphetamines, barbiturates, benzodiazepines, cannabinoids, cocaine, and opiates.

Cotinine Test: Test for nicotine.

Alcohol breath test: This will be performed locally at screening only.

Instruction on urine and blood sample processing and shipping are available in the laboratory manual.

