## After Dosing:

- Collect vital signs (blood pressure, heart rate, respiratory rate, temperature, oxygen saturation) and record 2 hours (±30 minutes) after dosing.
- Dispense trial treatment to take home.

The subject will take the second dose of trial treatment at home before bedtime and will continue to take the randomized treatment twice daily for 14 days.

#### 5.2.2.5 Treatment Period Procedures - Visits 4 and 8

This visit may be conducted at the clinic or at another location such as the subject's home, according to the preference of the subject.

The following assessments and procedures will be performed:

- Collect vital signs (blood pressure, heart rate, respiratory rate, temperature, and oxygen saturation).
- Record changes in concomitant medications.
- Symptomatic physical examination may be performed, if deemed necessary (e.g., to record any changes since screening or due to an AE). This may require an additional visit to the investigative site.
- Record any AEs since the last visit.

CONFIDENTIAL Page 33 of 68

Subjects should be fitted with a cough recorder by 10:00 am. The cough recorder must be worn for 24 hours between fitting and disconnection. The subject will take the trial treatment at home before bedtime and will continue to take the randomized treatment twice daily.

## 5.2.2.6 Treatment Period Procedures - Visits 5 and 9

The following assessments and procedures will be performed:

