# Before Dosing:

- Collect vital signs (blood pressure, heart rate, respiratory rate, temperature, and oxygen saturation).
- Record changes in concomitant medications.
- Symptomatic physical examination may be performed, if deemed necessary (e.g., to record any changes since screening or due to an AE). This may require an additional visit to the investigative site.
- Record standard 12-lead ECG.
- Collect blood sample for routine laboratory testing (biochemistry and hematology).
- Collect urine sample for urinalysis and urine/creatinine ratio.
- Perform urine pregnancy test (women of childbearing potential).
- Record cough severity VAS.
- Complete LCQ.
- Complete COLO.
- Record global rating of change for cough severity and frequency, PGIC, CGIC.
- Record any AEs since the last visit.
- The cough recorder will be disconnected 24 hours after fitting and retained by the investigative site.

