## After Dosing:

• Collect vital signs (blood pressure, heart rate, respiratory rate, temperature, oxygen saturation) and record at 2 hours (±30 minutes) after dosing.

Subjects will be instructed to take the last dose of trial treatment in the evening at the usual time.

## 5.2.2.7 End-of-Trial visit - Visit 10

The following assessments and procedures will be performed at the clinic:

- Collect vital signs (blood pressure, heart rate, respiratory rate, temperature, and oxygen saturation).
- Record changes in concomitant medications.
- Conduct physical examination, including review of the major body systems.
- Record standard 12-lead ECG.
- Collect blood sample for routine laboratory testing (biochemistry and hematology).

CONFIDENTIAL Page 34 of 68

- Collect urine sample for urinalysis and urine/creatinine ratio.
- Record any AEs since the last visit.
- Unused trial medication and empty containers from Treatment Period 2 will be collected or returned.

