## 5.2.2.8 Early Withdrawal Visit Procedures

If a subject withdraws/is withdrawn from the trial, the following assessments should be performed:

- Collect vital signs (blood pressure, heart rate, respiratory rate, temperature, and oxygen saturation).
- Record changes in concomitant medications.
- Conduct physical examination, including review of the major body systems. This may require an additional visit to the investigative site.
- Record standard 12-lead ECG.
- Collect blood sample for routine laboratory testing (biochemistry and hematology).
- Collect urine sample for urinalysis and urine/creatinine ratio.
- Record cough severity VAS.
- Complete LCQ.
- Complete CQLQ.
- Record global rating of change for cough severity and frequency, PGIC, CGIC.
- Record any AEs since the last visit.
- Unused trial treatment and empty containers will be collected or returned.

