## 6.5 Removal of Subjects from Therapy or Assessment

Participation in the trial is strictly voluntary. A subject has the right to withdraw from the trial at any time and for any reason. If they choose to withdraw from the trial, the Investigator must be informed immediately. The Investigator has the right to terminate participation of any subject at any time if it is in the subject's best interest. The reason and circumstances for premature discontinuation will be documented in the subject's electronic case report form (eCRF).

A subject may be discontinued from treatment for any of the following reasons:

- Withdrawal of consent by the subject.
- Severe lack of compliance with trial treatment in Treatment Period 1 (i.e., <80% or >120% compliance).
- Increase from baseline in serum creatinine by  $\geq 0.3$  mg/dL or  $\geq 50\%$ .
- Major protocol deviation, e.g., requirement for a disallowed concomitant medication or non-drug therapies (see Table 3, Section 10.1.2).

CONFIDENTIAL Page 38 of 68

- Trial treatment must be discontinued in subjects who become pregnant in the trial. The pregnancy will be reported and followed up as per guidance in (see Section 8.3.2). However, the subject should still undergo relevant post-randomization procedures and visits if possible and safe to do so.
- Investigator's decision that it is not in the best interest of the subject to continue.
- Lost to follow-up: The subject stopped coming to the investigative site for visits, and trial personnel were unable to contact the subject.

Immediate safety concerns should be discussed with the Sponsor immediately upon occurrence or awareness to determine if the subject should continue or discontinue trial treatment.

If possible, an early termination visit should be conducted (i.e., procedures for the end of Treatment Period 1 Visit 4 or Treatment Period 2 Visit 8). The subject will be permanently discontinued from the trial treatment but will continue to be observed for AEs, if possible, until the scheduled end-of-trial visit (Visit 10).

If the subject withdraws consent for disclosure of future information, the Sponsor may retain and continue to use any data collected before such a withdrawal of consent.

If a subject withdraws from the trial, they may request destruction of any samples taken and not tested, and the Investigator must document this in the investigative site trial records.

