## 8.3 Early Withdrawal Assessments

Early withdrawal assessments of efficacy parameters; cough severity, Leicester Cough Questionnaire (LCQ), Cough Quality of Life Questionnaire (CQLQ), Global Rating of Change, Patient Global Impression of Change (PGIC), and Clinician Global Impression of Change (CGIC), as well as safety laboratory and ECG assessments, will be analyzed with the Day 14 assessments of the relevant withdrawal period if treatment is administered for that period. Early withdrawal assessments will be listed as Early Withdrawal.

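### Protocol 6.5 sends early leavers to visits with no listed laboratory tests or ECG, contradicting 5.2.2.8 and SAP 8.3; the pregnancy-test lists also need aligning

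*Protocol*

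**What the plan says.** **Early termination.** Two protocol sections describe the visit. Section 5.2.2.8 opens with "If a subject withdraws/is withdrawn from the trial, the following assessments should be performed" and then lists ECG, blood, urine, the cough severity VAS, LCQ, CQLQ and the global ratings, among others. Section 6.5 instead asks, if possible, for "procedures for the end of Treatment Period 1 Visit 4 or Treatment Period 2 Visit 8". Visits 4 and 8 are described in 5.2.2.5: vital signs, medication changes, an examination only if judged necessary, adverse events, and fitting of the cough recorder.

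Protocol 5.1 asks subjects who stop treatment to attend an early-termination visit as soon as possible. It drops the later follow-up safety assessment if that visit falls more than 1 week after the last dose.

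SAP 8.3 states that early-withdrawal efficacy questionnaires, "as well as safety laboratory and ECG assessments, will be analyzed with the Day 14 assessments of the relevant withdrawal period", provided treatment was given in that period.

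**Pregnancy tests.** Section 8.3.3 gives a serum test at screening and "urine pregnancy tests before the first dose at the start of each treatment period (Visit 3 and Visit 7". The visit lists go further. Under Visits 5 and 9 (5.2.2.6), the pre-dose list on Day 14 also contains "Perform urine pregnancy test (women of childbearing potential". After that visit, "Subjects will be instructed to take the last dose of trial treatment in the evening at the usual time". The lists for Visit 10 (5.2.2.7) and early withdrawal (5.2.2.8) include a urine sample but no pregnancy test.

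The Schedule of Assessments (Table 1) is blacked out in the SAP and not visible in the protocol.

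**The concern.** The primary objective is safety, and Protocol 4.2.1 makes laboratory and ECG changes primary-endpoint measures. Subjects who stop early are those whose safety data matter most. One listed reason for stopping in 6.5 is a rise in serum creatinine, yet read literally the same section sends that subject to a visit with no listed blood sample.

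The pregnancy-test text has a smaller problem of the same kind. Section 8.3.3 disagrees with 5.2.2.6. The protocol also treats the weeks after dosing as relevant: pregnancies within 4 weeks of the last dose must be reported (8.3.2), and contraception continues for at least 30 days (7.9.2). No visible list places a test in that window after Period 2 or after early withdrawal.

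**Working it through.** **Step 1: compare the two early-termination lists.** Inputs: Protocol 5.2.2.8, Protocol 5.2.2.5 and SAP 8.3.

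| Item in 5.2.2.8 | Listed at Visits 4/8 | Named in SAP 8.3 |
|---|---|---|
| Vital signs | yes | no |
| Medication changes | yes | no |
| Physical examination | only if judged necessary | no |
| Adverse events | yes | no |
| ECG | no | yes |
| Blood sample | no | yes (safety laboratory) |
| Urine sample | no | yes (safety laboratory) |
| Cough severity VAS | no | yes |
| LCQ | no | yes |
| CQLQ | no | yes |
| Global ratings, PGIC, CGIC | no | yes |
| Return of unused treatment | no | no |

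Absent under 6.5: 12 − 4 = 8 items. Of these, 8 − 1 = 7 are data that SAP 8.3 plans to analyze. The SAP therefore matches 5.2.2.8 and not 6.5. The one thing Visits 4/8 add is the cough recorder, and SAP 8.3 does not name cough frequency among its early-withdrawal data.

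**Step 2: can a later visit recover the data?** Visit 10 collects ECG, blood and urine, but 5.1 waives follow-up when early termination is more than 1 week after the last dose. When Visit 10 does take place, SAP 15.2 and 15.5 summarize it overall against study baseline, so it does not replace a Day 14 value by treatment. Unscheduled tests are allowed (Protocol 8.3), but SAP 8.4 keeps post-baseline unscheduled values out of the summaries.

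**Step 3: how many subjects?** The visible text gives no dropout rate. Assume 5% to 10% stop before Day 14 of their ADX-629 period: 50 × 0.05 = 2.5 and 50 × 0.10 = 5 subjects. This is a ceiling, since it requires every site to follow 6.5 over 5.2.2.8.

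**Step 4: timing of the visible pregnancy tests.**
- Doses per period: 14 × 2 = 28. The Visit 9 test precedes both Day 14 doses, so 28 − 2 = 26 come before it.
- After Period 1, a washout of 14 ± 2 days puts the Visit 7 test about 12 to 16 days after the last dose.
- After Period 2, the visible lists show none. Visit 10 is about 14 days after the last dose (Protocol 5.1), or Day 29 in SAP 9, so a test there would fall about 14 to 15 days after the Visit 9 test. SAP 4 gives 1 to 2 weeks for this visit; I use the protocol, which sets the visits.

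**Step 5: how many women?** The documents give no figures. Assume 60% to 75% women and 10% to 40% of them of childbearing potential. The low end reflects Protocol 3.1, which describes patients as mostly women aged 45 to 75.
- Women of childbearing potential: 50 × 0.60 × 0.10 = 3, up to 50 × 0.75 × 0.40 = 15.
- Given ADX-629 second, taking half: 1.5 to 7.5.
- Stopping before Day 14 of their ADX-629 period: 3 × 0.05 = 0.15, up to 15 × 0.10 = 1.5.

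Even with 15 women, an expected count of one missed pregnancy would need a chance of 1/15, about 6.7%, for each within a few weeks on required highly effective contraception. The realistic expectation is far below one.

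**The case against.** **6.5 may mean the end-of-period visit pair.** End-of-period visits run over consecutive days, and SAP 12.1.1 labels Visit 4 as the end of Period 1 and Visit 8 as the end of Period 2. Read as Visits 4–5 or 8–9, section 6.5 would bring in ECG, blood, urine and a pregnancy test. This is possible, and a wrong visit number is a likely explanation. But 6.5 names only Visits 4 and 8, and a site cannot be expected to infer the rest.

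**6.5 may cover stopping treatment, and 5.2.2.8 leaving the trial.** Section 6.5 also covers withdrawn consent and loss to follow-up. If the distinction were intended, subjects who stop treatment would have no listed laboratory tests or ECG at early termination.

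**5.2.2.8 already requires the data.** This stands. A reader might infer that early leavers have no planned laboratory tests or ECG. The documents do not support that: two instructions conflict, and data are lost only where a site follows 6.5.

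**Table 1 may contain the pregnancy tests.** This also stands. Section 8.3.3 defers to Table 1 for timing. The visit lists are not exhaustive: the screening list omits the cotinine test that exclusion 1 needs. The synopsis counts pregnancy testing among laboratory parameters, and 5.1 says the end-of-trial visit covers laboratory parameters. Other visits list the pregnancy test separately, so this leaves the question open. A reader might infer that no pregnancy test is done after exposure ends; a missing bullet beside a redacted schedule cannot show that.

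**A later test is a preference.** Largely so. Women are tested on the last dosing day, the reported half-life is 3.49 to 6.83 hours, and contraception and pregnancy reporting both continue after dosing. No document requires a test at Visit 10.

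**Conclusion.** Section 6.5 conflicts with 5.2.2.8 and with SAP 8.3, whatever Table 1 contains. Followed literally, it omits 8 of 12 early-withdrawal items, including laboratory and ECG measures that belong to the primary endpoints. The loss is complete when 5.1 also waives follow-up. On the stated dropout assumption, at most 2.5 to 5 of 50 subjects would be affected in their ADX-629 period.

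The mismatch between 8.3.3 and 5.2.2.6 is also plain in the text. The absence of a pregnancy test at early withdrawal and Visit 10 is established only for the visible lists. It touches few women on assumed proportions, with far fewer than one missed pregnancy expected. Nothing here changes an efficacy result, the sample size or the error rate. It is a low-severity correction worth making because it is nearly free.

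**What to change.** 1. In 6.5, replace the reference to Visit 4 and Visit 8 procedures with a reference to 5.2.2.8.
2. In 8.3.3, list the urine pregnancy tests as Visits 3, 5, 7 and 9, to agree with 5.2.2.6.
3. Check Table 1. Unless it already has them, add a urine pregnancy test for women of childbearing potential at early withdrawal (5.2.2.8) and at Visit 10 (5.2.2.7), and carry both into 8.3.3 and Table 1. If Table 1 already has them, only the text needs aligning.

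The cost is a short amendment and about one extra urine test per woman of childbearing potential: 3 to 15 in all on the assumptions above, or two for an early leaver who also attends Visit 10. The urine is already collected at both visits. SAP 8.3 needs no change.
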